6.0 CLINICAL RESEARCH PLAN

6.1. STUDY POPULATION

Six DMD subjects age 7 years and older with confirmed DMD gene mutations based on mutation will be enrolled at Nationwide Children's Hospital for the gene transfer study. Subjects will encompass any ethnic or racial background.

6.2. PRE-TREATMENT ASSESSMENT

A. Establish Subject Eligibility

I. Inclusion Criteria

- 1. Age 7 or older
- 2. Confirmed DMD gene mutations
- 3. Impaired muscle function based on clinical evidence including difficulty climbing stairs, getting from the floor (Gowers' sign), and weakness of individual muscles of extremities
- 4. Males of any ethnic group will be eligible
- 5. Ability to cooperate with study procedures including muscle testing.
- 6. Willingness of sexually active subjects with reproductive capacity to practice reliable method of contraception
- 7. Subjects must be on stable dose of prednisone or deflazacort for three months at time of enrollment. Subjects will continue the steroid dose post gene transfer as part of the standard of care for DMD patients. Dose adjustment could be considered if there are adverse effects.

II. Exclusion Criteria

- 1. Active viral infection based on clinical observations.
- 2. The presence of a DMD gene mutation without weakness or loss of function
- 3. Symptoms or signs of cardiomyopathy, including:
 - Dyspnea on exertion, pedal edema, shortness of breath upon lying flat, or rales at the base of the lungs
 - Echocardiogram with ejection fraction below 40%
- 4. Serological evidence of HIV infection, or Hepatitis A, B or C infection
- 5. Diagnosis of (or ongoing treatment for) an autoimmune disease

- 6. Concomitant illness or requirement for chronic drug treatment that in the opinion of the PI creates unnecessary risks for gene transfer
- 7. Subjects with rAAV1 binding antibody titers > 1:50 as determined by ELISA immunoassay
- 8. Abnormal laboratory values for liver, kidney, CBC, in the clinically significant range, based upon normal values in the Nationwide Children's Hospital Laboratory

System	Assay	Normal Range	Abnormal (Clinically Significant)
Liver Function	GGT	8-80 U/L	>3 times upper limit of normal
	Total Bilirubin	0.1-1 mg/dL	$\geq 3 \text{ mg/dL}$
Renal Function	Creatinine	0.3-1.3 mg/dL	>1.8 mg/dL
Hematologic	Hemoglobin	Age dependent	For all ages: $\leq 8 \text{ or } \geq 18 \text{ g/dL}$
Hematologic	White Blood Cells	Age dependent	For all ages: $\leq 3.5 \text{ or } \geq 20 \text{ x } 10^3 \text{ cells/mL}$ Or Absolute neutrophil count of $\leq 1.5 \text{ x } 10^3$ cells/mL

B. Informed Consent

Legally effective and properly executed written informed consent, in compliance with 21 CFR 50 and the International Conference on Harmonization (ICH) guidelines, will be obtained from each subject before the subject is entered into the trial or before any unusual or non-routine procedure is performed that involves risk to the subject.

Attention will be directed to the basic elements that are required for incorporation into the informed consent under US Federal Regulations for Protection of Human Subjects [21CFR 50.25(a)]. The final IRB-approved document as well as any subsequent approved modified consent document(s) must be provided to correspondent agencies for regulatory purposes. If new information related to the study arises, subjects will be asked to sign a revised document. Signed consent forms will remain in each subject's research chart and be available for the verification by study monitors at any time. Subjects will be given a signed, dated copy of their consent form documents.

C. Establish Subject Identification Number

All subjects will be given a unique sequentially assigned subject number. Subjects will be identified by number only to protect identity.

D. Baseline/Screening Assessment (day-45 to day -1)

After obtaining informed consent and completing the registration procedures a baseline patient history will be collected, including records of all medications and supplements that the patient is taking. The following assessments will be performed to confirm subject eligibility for this study. Baseline tests which must be completed prior to treatment administration include the following:

Day -45 to day -1 before gene transfer

- Medical history
- Physical exam
- EKG
- ECHO
- Chest X-ray
- MRI of the gluteal muscles, quadriceps and TA (should not be repeated if the patient had the MRI test done within the previous year)
- Hepatitis A,B, &C Screen
- HIV screening
- CBC/Diff/Platelet with smear
- Total Protein
- Alanine transaminase (ALT)
- Aspartate Aminotransferase (AST)
- Serum gamma-glutamyl transferase (GGT)
- Total bilirubin
- Glucose
- Creatine kinase (CK)
- Creatinine
- BUN
- Cystatin C
- Alkaline phosphatase
- Amylase
- Prothrombin time (PT), partial thromboplastin time (PTT)
- Urinalysis
- Neutralizing antibody and/or binding antibody to AAV1
- ELISA assay to detect antibody to follistatin
- ELISPOT assay to detect T cell response to AAV1 capsid proteins and follistatin
- Quantification of blood circulating follistatin
- Six minute walk test (6MWT), functional and strength measures by PT
- Life quality questionnaire
- Pulmonary Function Test (PFT)
- Electrical Impedance Myography (EIM) to quantify pathological status of muscles: Skulpt, Inc. has developed a handheld device specifically for performing EIM measurements. This device will be used to measure EIM in this study. The device is not yet approved by FDA, but has been tested in over 30 other individuals with no adverse events (AEs) (serious or otherwise) reported to date and currently being tested in SMA infants as part of the Network for Excellence in Neuroscience Clinical Trials

(NeuroNEXT) trials, and SMA gene therapy trial. The device has undergone independent electrical safety testing by Intertek (www.intertek.com) to the requirements contained in the following standards:

IEC 60601-1 Issue 1998/12/01 Ed: 2 Medical Electrical Equipment Part 1: General Requirements and Safety; (Amd. 1-1991(CENELEC EN 60601-1: 1990) (Amd. 2-1995) (Corrigendum-1995))

- Baseline muscle biopsy on quadriceps muscles of one leg
- Subjects will be instructed to perform strengthening/endurance exercises at home 3 times per week, and asked to report the frequency of exercise. They will be incentivized through a video game and it will be emphasized that this should be relatively mild effort. The subjects will be incentivized to complete the exercise program by offering them \$10 per week for completion of log showing that exercise has been done.

* Study participants will continue prednisone post gene transfer as part of the standard management of DMD boys. Glucocorticoids are considered standard of care for DMD and most boys will be on a steroid regimen at the time they are recruited.

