6.5 ASSESSMENT OF ENDPOINTS

A. Safety monitoring post-gene transfer

Monitoring will occur on Study Days 1, 7, 14, 30, 45, 60, 90,180, and continue at 9, 12, 18, and 24 months post gene transfer. The following parameters will be included at different time points during the monitoring evaluations (see study timeline section 6.7):

- Physical Exam
- ALT
- AST
- GGT
- Total bilirubin
- Glucose
- PT/PTT
- CBC/Diff/Platelet with smear
- Serum Creatine kinase (CK)
- Creatinine/BUN
- Cystatin C
- Alkaline phosphatase
- Amylase
- Total Protein
- Urinalysis
- Blood antibody to AAV1 and follistatin
- ELISPOT assay to detect T cell response to AAV1 capsid proteins and follistatin
- Blood circulating follistatin
- Photograph of injection site/ surrounding area
- Adverse events
- Pulmonary Function Test (PFT)

B. Efficacy Monitoring

I. Primary Outcome

Safety is a primary outcome for this clinical gene transfer trial.

II. Secondary Outcomes:

- The distance walked on the 6MWT is the primary functional outcome to be evaluated. Time to walk and run, strength test, functional test, and reaching ability will be included in PT testing. Functional testing will be performed at baseline and at days 30, 60, 90,180, and 9, 12, 18 and 24 months post-gene transfer.
- Life quality questionnaire will be completed at baseline and 6, 12, 18 and 24 months post-gene transfer.
- In order to maximize potential benefit of follistatin gene therapy, subject will be instructed to continue strengthening exercise at home at least 3 times per week as instructed by physical therapists (PT), and asked to report the frequency of exercise. The subjects who follow the exercise instruction will be incentivized by video display and offered \$10 per week if they fill out their log showing bike riding complete.
- MRI studies of leg muscles will be done pre and post gene transfer (6, 12 and 24 months) to study muscle size, fibrosis and fat content.
- EIM measurement will quantify the pathological status of muscles.
- Muscle biopsies on quadriceps muscles (a muscle biopsy on one leg at baseline screening visit and the post gene transfer biopsy on the opposite leg at day 180), will include general histological evaluation. Assessment will consist of morphometric analyses for quantification of fiber size, fibrosis, inflammatory process, satellite cells and regeneration. Muscle tissue obtained at biopsy will also be assessed for viral DNA (qPCR), and follistatin transgene expression

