6.6 STATISTICAL ANALYSIS

This is a phase I/IIA trial, with safety as the primary measure. For each measure based on differences between pre- and post-gene transfer examinations (clinical) analyses will be based on a paired t test, with a p value of < 0.05 indicating significance.

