6.7 STUDY TIMELINE

STUDY TIMELINE																
Study Interval	Baseline Screening	In	/ecto jection patie	on	Follow Up (Outpatient)											
Visit	1	2			3	4	5	6	7	8	9	10	11	12	13	14
Days in Study	-45 to -1	-1	0	1	7	14	30	45	60	90	180	194*	9 mo	1 yr	18 mo	2 yr
Informed Consent	x															
Medical History	Х															
Physical Exam & vitals	x	x		x	x	х	х	х	х	x	x	х	х	х	х	x
ECHO/EKG	x															
Chest X-Ray	х															
MRI	х										х			Х		х
Hepatitis A, B & C HIV	x															
Safety labs	Х			Х	Χ	Х	Х	Х	Х	Х	Х					
Urinalysis	x			х	х	х	х	х	х	х	х					
Pulmonary function test	x						х			x	x		х	х		
PT evaluation	x						х		х	х	х		х	х	х	х
Life quality questionnaire	x										x			х	х	x
EIM	х									х	х			Х		
Immunology studies	x				x	x	х	х	x	x	x		x	x	x	x
Circulating follistatin	x						x			x	x		x	x	x	x
Gene Transfer			х													
Muscle Biopsy	x										х					
Photograph of injection site			x	x	x	x	х	x	x	x	x	x	х	x	x	x
Adverse Events			х	х	х	Х	Х	Х	х	х	х	х	Х	х	х	х
Concomitant Medications	To be collected from time of consent until final study visit, recorded on separate CRF															

Note: There will be a flexibility of a +/-7 working days for each of the planned study visits including screening to adjust the schedule to any unanticipated event. There will also be potential additions to care based on best medical management if the need arises including additional fluids to restore blood volume.

*: The follow up post-biopsy visit scheduled 2 weeks post-biopsy is made optional to give subjects the choice to have the stiches removed at their local doctor's office.

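### Does the unstated order of the baseline walk test, biopsy and exercise start, or the unused exercise log, call for a change to the plan?

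*Combined protocol and SAP*

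**What the plan says.** The baseline list in section 6.2 D is headed "Day -45 to day -1 before gene transfer". It contains the 6MWT with the physical therapy measures, then "Baseline muscle biopsy on quadriceps muscles of one leg", and last the exercise item: "Subjects will be instructed to perform strengthening/endurance exercises at home 3 times per week, and asked to report the frequency of exercise". On intensity it adds that "it will be emphasized that this should be relatively mild effort". The only timing rule is that baseline tests be finished before treatment. The list is not said to be a sequence.

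In section 6.7 the row "PT evaluation" has one mark before transfer, in the day -45 to -1 column, which is numbered Visit 1. The biopsy is marked in the same column, and both are marked again at day 180.

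Section 6.5 B says "The distance walked on the 6MWT is the primary functional outcome to be evaluated", places it among the secondary outcomes, and tests it at baseline and at eight visits from day 30 to 24 months. It gives the exercise instruction after transfer: "to maximize potential benefit of follistatin gene therapy, subject will be instructed to continue strengthening exercise at home at least 3 times per week". The synopsis and section 6.5 B both put the first biopsy at the screening visit, in the singular.

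Section 6.6 names safety as the primary measure and says of pre/post measures that "analyses will be based on a paired t test, with a p value of < 0.05 indicating significance". It mentions neither exercise nor the log.

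**The concern.** All six boys are treated, so the change in 6MWT is the net of vector, exercise, practice and disease course. The single baseline walk enters every one of the eight post-transfer changes. If that walk follows a thigh biopsy, for which section 11.2.2.3 warns of pain, the baseline may be low and the change inflated. If it follows some weeks of exercise, the baseline may be high and the change shrunk. If practice differs between boys, the baseline does not mean the same thing for each. Day 180 raises the same question about biopsy and walk.

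The exercise wording also differs across transfer: three sessions a week at mild effort before, at least three afterwards with the aim of maximising benefit. A frequency log is collected and paid for, yet has no stated use. At stake is how far a reported gain or loss in walking distance can be read as a drug effect.

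**Working it through.** The plan gives no power, effect size or SD for the 6MWT, so there is no figure of its own to reproduce. The check is mainly textual, with arithmetic for scale.

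**How much exercise could precede the baseline walk.** The extreme is instruction on day -45 and the walk on day -1: 44 / 7 × 3 = 18.9 sessions. That requires Visit 1 to be spread over the whole window. The documents do not exclude it, but they point the other way: the biopsy belongs to one screening visit, the timeline has one visit number, and the exercise is a home instruction placed after every test. If screening is one visit, no home session precedes the walk. The order of walk and biopsy within that visit is then the main open point.

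**Whether exercise steps up at transfer.** Section 6.5 B asks boys to continue, which describes the same programme. Three and at least three are close, the mild-effort instruction is not withdrawn, and the benefit clause explains why exercise goes on. An increase is possible but cannot be inferred from this wording.

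**Scale of a baseline shift.** The mean change is mean(post) minus mean(pre), so a shift of d metres in every boy moves it by d, and in one boy by d / 6. The half-width of a 95% confidence interval is 2.571 × SD / √6 (t, 5 df). The only changes available are the Becker results in section 7.2: 58, 125, 9, 108 and 29 m, plus one patient without improvement whose figure is not given.

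| Assumed sixth value | Mean | SD | Half-width | 10 m shift | 20 m shift |
|---|---|---|---|---|---|
| 0 m | 54.8 m | 52.0 m | 54.6 m | 18% | 37% |
| -50 m | 46.5 m | 65.0 m | 68.2 m | 15% | 29% |

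The 10 and 20 m are assumptions, and the SDs come from another disease at lower doses. A shift in one boy only gives 10 / 6 = 1.7 m to 20 / 6 = 3.3 m on the mean.

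**What the possible remedies would gain.**
- *Fix the order.* Walk before biopsy is what a site would do unprompted. Walk before exercise is debatable: it places the whole exercise effect in the pre/post change, while the reverse order removes only the part that appears before transfer. Neither separates exercise from vector.
- *Add a walk at day -1.* If the screening walk came first, the day -1 walk would always follow both biopsy and exercise start. The difference would mix practice, exercise and recent biopsy, possibly with opposite signs. For an assumed SD of that difference of 15 to 40 m, its half-width is 2.571 × 15 / √6 = 15.7 m to 2.571 × 40 / √6 = 42.0 m, against a shift of 10 to 20 m to be detected. Two baselines at eight visits make 16 contrasts with none named as the main one. The two-week interval in section 6.7 concerns stitch removal, so it gives no rule for when a walk after biopsy is valid.
- *Use the log.* Six self-reported, paid logs support a listing beside each boy's change, not an adjustment. A listing alters no test result.

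**The case for a change.** The best case for a change is that it is nearly free. Stating the order takes a sentence, and with six boys each one is a sixth of the mean. The synopsis names walking distance in its objectives next to safety, and section 6.6 attaches a significance threshold to it. If an artefact adds 20 m to every change and the vector does nothing, the chance of a significant gain is 26.5% at SD 30 m, 12.4% at SD 50 m and 8.3% at SD 70 m, against a nominal 2.5% in that direction.

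The omissions are real and the arithmetic is right. But those chances require the same 20 m in all six boys, a figure with no source in the documents. They would hold equally for exercise, practice or disease course after transfer, which no ordering of the screening tests removes. That limit comes with any single-arm study of six, and section 6.6 makes no claim that a change is due to the vector alone. What stands is a point of clarity about whether the walk comes before the biopsy at two visits.

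**Conclusion.** No change is called for. The missing order is a detail that a site fills sensibly, and the missing use of the log is a gap that an analyst fills with a listing from data already collected. The one remedy that would add information, a second baseline walk, would give a mixed and imprecise quantity at the cost of six more tests. The documents establish neither size nor direction of bias; on the assumed 10 to 20 m in every boy it is 15% to 37% of the interval's half-width, and less if only some boys are affected. The point touches a secondary outcome and leaves the safety aim alone.

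This rests on reading screening as essentially one visit with the walk done before the biopsy, which the singular wording supports but does not state, and on reading the 6MWT result as the net change in an uncontrolled study.

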6.3 PROTOCOL FOR GENE TRANSFER

I. Injection preparation

Preparation of the rAAV1.CMV.huFS344 will be in the investigational drug service based on the drug order from and following pharmacy standard protocol. The vector shall be diluted and manipulated in polypropylene syringes only. Polystyrene and polycarbonate materials should never come in contact with the vector.

Prior to transportation to the clinical setting appropriate dilutions of the test article will be completed by the pharmacy. The dose will be diluted in normal saline, divided in 9 ml per leg with 0.5 ml delivered per site on each leg. Documentation of the dilution will be completed by the pharmacy following standard pharmacy protocol. The formulated syringes will be maintained refrigerated at 2-8C until transport to the patient procedure room where it will be delivered on wet ice in the appropriately labeled cooler.

The final volume delivered to the PI will be 18 ml total volume distributed in 18 polypropylene syringes of 1 ml each, nine syringes being delivered to the right leg and nine to the left leg. The vector-containing syringe will be delivered to the designated procedure room at Nationwide Children's Hospital. It will be delivered on wet ice (not frozen) and administered to the subject within 8 hours of of thaw. Handling of rAAV1.CMV.huFS344 will follow compliance standards

for Biosafety Level 1 vectors. (http://www4.od.nih.gov/oba/RAC/guidelines 02/APPENDIX G.htm# Toc7246561)

II. Vector Administration Protocol

Conscious sedation will be given to all DMD participants by an anesthesiologist who will be with patient at the time of injection. In addition, the skin over the gene transfer site will be pre-treated with a lidocaine/prilocaine eutectic mixture incorporated in a cream base (EMLA cream) or a cellulose disk (EMLA patch). Comparable cream-based anesthesia such as xylocaine cream might be used. Procedures will be performed under sterile conditions. The injection site will be cleansed with three successive applications of non-iodine containing surgical prep swabs and draped with disposable sterile drapes. A standard clinical Doppler ultrasound will be used with a sterile sheath around the transducer to maintain asepsis of the injection field. This will increase the precision of gene transfer to be sure that we inject muscle and not connective tissue or fat.

The total dose of vector per extremity, $1.2 \times 10^{12} \text{ vg/kg}$ will be distributed between the targeted muscles that include gluteals, quadriceps, and tibialis anterior. The initial sites of injection, at least three injections per muscle, will be targeted based on MRI showing preserved muscle. The sites will be confirmed at the time of injection by ultrasound guidance for the needle injections. The procedure should take approximately 30 minutes to inject muscles of both extremities.

6.4 POST GENE TRANSFER MONITORING

6.4.1 IMMEDIATELY FOLLOWING GENE TRANSFER

Vital signs including blood pressure, heart rate, respiratory rate and temperature will be performed post-administration. Concomitant medications and all adverse events/serious adverse events will also be monitored and documented following injection. Patients will be discharged the day after gene therapy (if no side effects are observed).

6.4.2 FOLLOW UP

Subjects will return for follow up visits on days 7, 14, 30, 45, 60, 90,180, and 9, 12, 18, and 24 months post-gene transfer. Toxicity monitoring on each of these dates (including day 1 post-gene transfer) are described in the following sections of the protocol.

We will follow the most recent FDA guidelines with regard to long-term patient follow up following gene transfer. Our proposed vector has a very low probability of gene transfer-related delayed adverse events. We will, however, evaluate short-term safety over a two-year period that incorporates the active phase of the protocol (see assessment of endpoints below). If newly

identified risks are associated with our product, or if the patients suffer any adverse events during this period, we will initiate a long-term follow-up according to the FDA guidelines.

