8.0 ADVERSE EVENT MONITORING AND REPORTING

8.1 DEFINITION OF AN ADVERSE EVENT

As stated above this protocol will follow the final regulations issued by the Food and Drug Administration addressing the safety reporting requirements for investigational new drug applications (INDs) found in 21 CFR part 312 and for bioavailability and bioequivalence studies found in 21 CFR part 320. "Safety Reporting Requirements for INDs and BA/BE Studies".

http://www.fda.gov/downloads/Drugs/GuidanceComplianceRegulatoryInformation/Guidances/U CM227351.pdf

Adverse Events will be collected throughout the study from enrollment to last follow up visit.

Adverse Event (AE): Adverse event means any untoward medical occurrence associated with the use of a drug in humans, whether or not considered drug related.

Adverse events will be graded by the investigator accordingly:

Grade 1 Mild; asymptomatic or mild symptoms; clinical or diagnostic observations only; intervention not indicated.

Grade 2 Moderate; minimal, local or noninvasive intervention indicated; limiting age-appropriate instrumental ADL*.

Grade 3 Severe or medically significant but not immediately life-threatening; hospitalization or prolongation of hospitalization indicated; disabling; limiting self care ADL**.

Grade 4 Life-threatening consequences; urgent intervention indicated.

Grade 5 Death related to AE.

A Semi-colon indicates 'or' within the description of the grade.

A single dash (-) indicates a grade is not available.

Activities of Daily Living (ADL)

*Instrumental ADL refer to preparing meals, shopping for groceries or clothes, using the

telephone, managing money, etc.

**Self care ADL refer to bathing, dressing and undressing, feeding self, using the toilet, taking

medications, and not bedridden.

Association or relatedness to the study agent, study procedures and the subject's pre-existing disease will be graded as follows: 5 = unrelated, 4 = unlikely, 3 = possibly, 2 = probably, and 1 = definitely related.

Adverse reaction: An adverse reaction means any adverse event caused by a drug. Adverse reactions are a subset of all suspected adverse reactions for which there is reason to conclude that the drug caused the event.

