9.0 LONG-TERM FOLLOW UP

We will follow the most recent FDA guidance with regard to long-term patient follow up following gene transfer. As indicated by the guidelines, our proposed vector has a very low probability of gene transfer-related delayed adverse events. If newly identified risks are associated with our product, or if the subjects suffer any adverse events during this period, we will initiate a long-term follow-up according to the FDA guidelines. We will, of course, notify CBER if there is any indication of need to extend follow-up period. All subjects will be provided with written instructions on how to contact the Principal Investigator or study coordinator if they experience any serious adverse event that they consider possibly related to study treatment or study participation. This information will also be included in the Informed Consent document. All subjects will be instructed to notify the Principal Investigator of a change of address or contact information.

The final results of the clinical trial will be shared with the participants at the completion of the study when all data has been collected and analyzed. However, if significant findings become available that might increase the risk of the subjects or might affect their decision to remain in the study, then information will be made available as soon as it is available.

At the time of death, no matter what the cause, permission for an autopsy will be requested of their families. Subjects will be asked to advise their families of this request and of its scientific and medical importance.

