10.0 STUDY REPORTS

10.1 FINAL STUDY REPORT

The final study report will include data through the final study visit but will not include long-term follow-up information.

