11.2.1 RISKS ASSOCIATED WITH rAAV.CMV.HUFS344 GENE TRANSFER

There is a very small chance that the study agent could damage the DNA in the cells of the subject's muscle. In the unlikely event that this occurred, it could put the subject at risk for developing cancer in the future. In animal studies to date, we have not seen the development of cancer. In addition, we and others have shown that the majority of vector DNA appears to persist as episomal rather than integrated DNA, which makes it very unlikely that mutagenesis will occur.⁵⁴⁻⁵⁶ In summary, our data suggest that AAV genomes persist in mouse muscle as transcriptionally active large and small concatameric episomes and when considering potential and theoretical integration events, AAV vectors appear to possess a similar risk profile as plasmid DNA injected into muscle.⁵⁵ The majority of vector DNA appears to persist as episomal rather than integrated DNA, which makes it very unlikely that mutagenesis will occur.⁵⁴

Liver tumors were reported in one study performed in newborn mice at another center with a different rAAV vector. There is no evidence to indicate that these tumors were caused by

vector-induced DNA damage based on the number of AAV genomes per cell in tumor samples. ^{57, 58} Also, other larger scale studies in newborn and adult mice have not shown this effect. ⁵⁹ It remains difficult to ascertain the true risk of neoplasia, although it seems very small.

Subjects may also develop immune response to AAV1. This could lead to immune rejection of virus precluding gene expression. We will measure both binding antibodies and T cell responses to the AAV capsid following gene transfer.

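### After month 24, section 9.0 leaves the reporting of late serious events to the family's own view of cause, and the trigger for longer follow-up is unfiltered and ambiguous

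*Combined protocol and SAP*

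**What the plan says.** **Trigger.** The synopsis (long-term follow-up row), section 6.4.2 and section 9.0 give two routes to follow-up beyond the two-year study: a new risk identified with the product, or adverse events. Section 6.4.2 words the second as "if the patients suffer any adverse events during this period, we will initiate a long-term follow-up according to the FDA guidelines". Section 9.0 repeats it, but contains no two-year sentence for the phrase about the period to refer to. Section 8.1 defines an adverse event as "any untoward medical occurrence associated with the use of a drug in humans, whether or not considered drug related", with grades starting at mild or asymptomatic.

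**Reporting by families.** Section 9.0 gives subjects written instructions for contacting the team "if they experience any serious adverse event that they consider possibly related to study treatment or study participation", and says the same will appear in the consent form.

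**Capture during the study.** Section 8.1 states: "Adverse Events will be collected throughout the study from enrollment to last follow up visit". Section 9.1 asks families and primary care physicians to report all non-routine care, for the two years after gene transfer.

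**After the study.** The follow-up paragraph of section 8.3 sends a serious event to the FDA, NIH OBA, IRB and DSMB within 15 calendar days if it is judged to be associated with the product. Section 10.1 says the final report "will not include long-term follow-up information".

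**The delayed risk.** On possible vector damage to DNA, section 11.2.1 says "it could put the subject at risk for developing cancer in the future".

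**The concern.** Safety is the primary outcome, and the delayed risk the protocol names is cancer. Up to month 24, capture is broad and does not depend on anyone's opinion of cause. After month 24, the written instruction to families carries two conditions: the event must be serious, and the family must think it possibly related. Families of boys with DMD on long-term steroids have other explanations ready for a late illness. Section 8.3 then applies a second test of association before a post-study event goes to the agencies. That second test is for trained people to make, but they can make it only for events they hear about.

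The trigger is a separate weakness. A minor event in the first two years says little about who is at risk of a late cancer, yet it helps to decide whether anyone is followed. It is also unclear whether one boy's event starts follow-up for him alone or for all six.

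**Working it through.** The plan states no event rate, trigger probability or detection figure for this point, so there is nothing to reproduce. The check sets the rules side by side and then shows how the trigger behaves over a range of assumed rates.

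**1. Capture from living subjects**

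| | To month 24 | After month 24 |
|---|---|---|
| Adverse events at visits | All grades and causes (8.1) | No visits written |
| Non-routine care | All, from families and physicians (9.1) | Not requested |
| Instruction to families | 9.1, any non-routine care | 9.0, serious and thought possibly related |
| Onward reporting | Serious events to the DSMB whatever the relatedness (8.3) | Serious events judged associated with the product (8.3) |

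The change at month 24 is in what families are asked to report, not only in how often they are seen.

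**2. Trigger read as trial-wide**

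Inputs: n = 6 boys (synopsis; 11.0). Per-boy probability q of any adverse event in two years: not given, so assumed. Boys are treated as independent with a common q.

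P(at least one event) = 1 − (1 − q)^6

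- q = 0.05: 1 − 0.7351 = 26.5%
- q = 0.10: 1 − 0.5314 = 46.9%
- q = 0.30: 1 − 0.1176 = 88.2%
- q = 0.50: 1 − 0.0156 = 98.4%

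The probability reaches 95% at q = 1 − 0.05^(1/6) = 0.393.

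Section 3.0 says no adverse events were met in the earlier trials. Taken literally for the six Becker patients, zero of six still leaves a one-sided 95% upper limit of 1 − 0.05^(1/6) = 39.3% per patient, and those patients received lower doses (7.2). The documents therefore do not fix q.

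**3. Trigger read as per boy**

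Expected number of boys not followed = 6(1 − q). P(all six followed) = q^6.

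- q = 0.50: 3 boys not followed on average; all six followed in 1.6%
- q = 0.90: 0.6 boys; 53.1%
- q = 0.95: 0.3 boys; 73.5%

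A 95% chance that all six are followed needs q = 0.95^(1/6) = 0.991. All six receive the same vector at the same dose per kilogram (7.2), so a boy left out has no evident reason to carry a smaller delayed risk.

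**4. The family's judgement as a gate**

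Let a be the share of late serious events that families consider possibly related. Suppose those are reported and the rest are not. The share missed is 1 − a: 25%, 50% and 75% for a = 0.75, 0.50 and 0.25. These values are illustrations; the documents give no basis for a.

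**The case against.** The case on the other side is substantial, and much of it stands.

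- **Section 9.0 contains more than one provision.** It requests permission for autopsy whatever the cause of death, asks for updated contact details and promises notice to CBER if follow-up may need extending. There is also the new-risk route, and section 8.5 follows known events to resolution or stabilisation. All true. None of these asks a living boy about new events after month 24.
- **The threshold is low, and nothing forbids other reports.** The instruction says possibly related, and does not say that other events should be withheld. This limits the size of the gap. The family's view of cause still remains the stated condition.
- **Follow-up content is deferred to FDA guidance.** Once triggered, follow-up may include scheduled contact. This stands as a limit on the point: the guidance is not in the documents, so what it would require cannot be judged here.
- **A trigger that fires easily produces more follow-up, not less.** Correct. Frequent firing is not itself the harm. The weakness is that the trigger is unrelated to the late risk and can be read in two ways.

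Three stronger readings are tempting but unsupported. A reader might infer that the trigger is almost sure to fire. With no event rate given, and with 26.5% at the low end of the assumed range, the documents do not show that. A reader might see a conflict with the rule in section 8.3 that serious events go to the DSMB within 48 hours regardless of relatedness. That rule governs what the site passes on once notified, not what families tell the site, so the two do not contradict each other. A reader might treat the final report's exclusion of long-term data as a fault. A report that closes at the last visit naturally omits later data; what is needed is a stated place for them.

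**Conclusion.** The point holds for harm arising after month 24. The protocol makes the family's own opinion of cause the written condition for reporting a late serious event, just when the broader capture ends. A cancer attributed to DMD, steroids or chance could go unreported. How often cannot be estimated from the documents.

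Whether follow-up happens at all rests partly on an unfiltered adverse-event trigger with two readings. Trial-wide, it fires in 26.5% to 98.4% of trials for assumed per-boy rates of 5% to 50%. Per boy, it leaves out any boy without an early event. These figures assume independent boys with a common rate.

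This is a low-cost improvement to safety surveillance. It does not undermine the safety data collected during the two-year study.

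**What to change.** 1. In section 9.0, and in the matching consent text, ask families to report any serious adverse event or hospitalisation after month 24 whatever they believe caused it. Leave relatedness to the investigator.
2. In the synopsis and sections 6.4.2 and 9.0, replace the adverse-event trigger with one rule for all six boys: a brief scheduled contact, for example yearly, for the period in the FDA guidance the protocol says it follows. Name that guidance and state the period.
3. State where the data go: the section 10.2 annual reports or an addendum to the final report. Section 10.2 runs only until the trial is completed, so if the annual reports are used, say that they continue through long-term follow-up.

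The cost is an amendment to the protocol and consent wording plus, with yearly contact, about six brief contacts a year. The continuing effort is small, and the change to the family instruction costs almost nothing.
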